2.6 Analysis of the key secondary objective

There are no key secondary endpoints defined.

2.6.1 Key secondary endpoint**2.6.2 Statistical hypothesis, model, and method of analysis****2.6.3 Handling of missing values/censoring/discontinuations****2.7 Analysis of secondary efficacy objective(s)****2.7.1 Secondary endpoints****2.7.1.1 To evaluate the effect of symptoms as measured by the nasal congestion score with fevipiprant (150 mg or 450 mg once daily, separately) as compared to placebo, in terms of reduction in NCS from baseline to week 16.**

Nasal congestion is defined as the objective restriction of the nasal cavity airflow caused by mucosal pathology and or by mucosal secretions when anatomical variations have been excluded. The nasal congestion score is calculated based on the responses from the patients in Question 1 from the nasal congestion questionnaire. The questionnaire has four questions relating to the symptoms of nasal obstruction with each question having four categories ranging from 0-3, where the scores relate to the degree of severity as follows:

- 0 = Not at all
- 1 = Mild
- 2 = Moderate
- 3=Severe

The score however is calculated based on the response to the first question in the questionnaire.

2.7.1.2 To evaluate the effect on quality of life as measured by the sino-nasal outcome test (SNOT- 22) with fevipiprant (150 mg or 450 mg once daily, separately) , compared to placebo, in terms of increase in QoL score from baseline to Week 16.

SNOT-22 measures the quality of life in patients facing nasal obstructions (Section 16.5). There are 22 items available on the questionnaire. Each item in the questionnaire are followed by five options to choose from:

- 0 = No problem
- 1 = Very Mild Problem
- 2= Mild or slight problem
- 3= Moderate problem
- 4= Severe Problem
- 5 = Problem as bad as it can be.

The scores for each of the items are added to get a total out of 110, with 110 being the worst signifier of quality of life. The treatment group difference in terms of change from baseline at Week 16 in

2.7.1.3 To evaluate the effect on smell as measured by the university of Pennsylvania smell identification test (UPSIT) with fevipiprant (150 mg or 450 mg, once daily) ,compared to placebo, in terms of increase in smell score from baseline to Week 16.

The university of Pennsylvania smell identification test (UPSIT) is a test for smell identification to test an individuals olfactory response. The test is a measure of an individual's ability to detect odor. It consists of 4 workbooks of 10 questions, giving a total of 40 questions. On each page, there is a different "scratch and sniff" strip which are embedded with a microencapsulated odorant. There is also a four choice multiple choice question on each page. The scents are released using a pencil. After each scent is released, the patient smells the level and detects the odor from the four choices. There is an answer column on the back of the test booklet, and the test is scored out of 40 items. The score also indicates how the patient does in accordance to their age group and gender. The maximum score achievable on the scale is 40.

A sensitivity analysis would be performed excluding the patients from the sites for whom the UPSIT instrument was completed with pencil. This information would be recorded in the Data Handling Plan document.

2.7.2 Statistical hypothesis, model, and method of analysis

The treatment group difference in terms of change from baseline at Week 16 in UPSIT, SNOT 22 and Nasal Congestion Score will be estimated using an MMRM model with change from baseline as the response variable, and will be analysed similarly to the primary endpoint with appropriate baseline measurement .The least square mean change in scores for each of the questionnaires from baseline to week 16 alongside with 95% confidence interval and the P-value corresponding to the least square mean difference will be presented .

2.7.3 Handling of missing values/censoring/discontinuations

Despite all attempts to ensure complete follow-up for all patients, some patients may not be followed for nasal polyp size for the whole planned study duration of 16 weeks. The primary analysis will be done using a Mixed Model Repeated Measures (MMRM) approach. Under the assumption that the missing values are missing at random (MAR), this provides asymptotically unbiased and consistent estimates of the treatment effects.Safety analyses

2.7.4 To evaluate the general safety and tolerability of fevipiprant (150 mg and 450 mg, separately) as compared to placebo.

Safety and tolerability assessments would be based on the incidence of adverse events and serious adverse events, as well as vital signs, clinical laboratory evaluation, and 12-lead electrocardiogram findings.

For all safety analyses, the safety set will be used. All listings and tables will be presented by treatment group. Safety summaries will be primarily based on on-treatment data with selected tables also presented for all data after the first intake of study drug, while all databased safety data will be listed. The on-treatment period lasts from the date of first administration of study treatment to 1 day after the date of the last actual administration of any study treatment.

2.7.5 Adverse events (AEs)

Adverse events after informed consent including asthma exacerbations will be listed.

Adverse events starting on or after the day of the first intake of study drug and until the day after the last intake of study drug will be classified as treatment emergent adverse events. Adverse events that started during the study after informed consent and before the day of the first intake of study drug will be classified as prior adverse events and not included in tabulations of treatment emergent adverse events.

The number and percentage of patients who reported TEAEs will be summarized by primary system organ class (SOC), preferred term (PT), and treatment group for

- all adverse events (AEs)
- all AEs by maximum severity
- AEs suspected to be related to study drug
- AEs by standardized MedDRA query (SMQ) level serious AEs (SAEs)
- AEs leading to permanent study drug discontinuation
- Serious adverse events

Unless otherwise specified, primary system organ classes will be sorted alphabetically and, within each primary system organ class, the preferred terms will be sorted in descending order of frequency in the QAW039 150 mg once daily and QAW039 450 mg once daily treatment group. If a patient reported more than one AE with the same preferred term, the AE will be counted only once. If a patient reported more than one AE within the same primary system organ class, the patient will be counted only once at the system organ class level. In addition, the most frequent AEs will be presented by preferred term in descending order of frequency in the QAW039 150 mg QAW039 450 mg once daily treatment group.

Serious adverse events will also be summarized.

In addition, the most frequent AEs will be presented by preferred term in descending order of frequency in the QAW039 150 mg once daily treatment group.

All adverse events and related preferred terms and system organ class will be categorised using latest MedDRA version available at the time of data analysis.

2.7.5.1 Adverse events of special interest / grouping of AEs

The number and percentage of patients and treatment emergent adverse events of special interest will be summarized for each type of event with a break-down for each type of event by

SMQ(when applicable) and preferred term. The Compound Case Retrieval Strategy (CRS) will be used to determine the MedDRA search criteria to be used to identify events of special interest.

2.7.5.2 Adverse events reporting for safety disclosure

For the legal requirements of clinicaltrials.gov, two required tables on TEAEs which are not SAEs with an incidence greater than a certain threshold based on the final database and on treatment emergent serious adverse events and SAEs suspected to be related to study drug will be provided by system organ class and PT on the safety set population.

If for a same patient, several consecutive AEs (irrespective of study drug causality, seriousness and severity) occurred with the same SOC and PT:

- a single occurrence will be counted if there is ≤ 1 day gap between the end date of the preceding AE and the start date of the consecutive AE
- more than one occurrence will be counted if there is > 1 day gap between the end date of the preceding AE and the start date of the consecutive AE

For occurrence, the presence of at least one SAE / SAE suspected to be related to study drug / non SAE has to be checked in a block e.g., among AE's in a ≤ 1 day gap block, if at least one SAE is occurring, then one occurrence is calculated for that SAE.

The number of deaths resulting from SAEs suspected to be related to study drug and SAEs irrespective of study drug relationship will be provided by SOC and PT.

2.7.6 Deaths

A summary of deaths will be presented by primary system organ class, preferred term, and treatment groups regardless of study drug relationship.

All the deaths in the clinical database including those occurring during screening will be listed, but only those between the first treatment and the last dose + 1 day will be included in summary tables. Additionally all deaths after first dose of study treatment will be tabulated by treatment group.

2.7.7 Laboratory data

Laboratory data consist of hematology and biochemistry measurements. Laboratory data measured after first intake of study drug and until the day after last intake of study drug are regarded as on-treatment data. Laboratory data measured more than 1 day after last intake of study drug are regarded as post-treatment data and will not be summarized. All data will be listed with abnormal values flagged.

2.7.7.1 Summary of change from baseline

For continuous laboratory parameters, the on-treatment change from baseline to the worst post-baseline values (including values from post-baseline unscheduled and premature discontinuation visits) will be summarized by laboratory parameter and treatment group with standard descriptive statistics.

2.7.7.2 Notable values

For selected laboratory parameters, abnormalities occurring at any time-point over the treatment period, considering all post-baseline data from scheduled, unscheduled and premature discontinuation visits will be summarized. Patients with any newly occurring or worsening on-treatment value meeting the clinically notable criteria will be counted under the applicable criteria.

For a patient to meet the criterion of a newly occurring clinically notable value, the patient needs to have a baseline value which is not clinically notable for that parameter. For a patient to meet the criterion of a worsening clinically notable value, the patient needs to have a baseline value which is not clinically notable and also have a worse post-baseline value. For patients with a missing baseline value, any post-baseline notable value will be considered as newly occurring.

The criteria for clinically notable values are presented in [Table 5.3.2](#).

Laboratory test units will be converted to standard units. Based on agreement within our standards, if we have a multi-region study the Blood Urea Nitrogen (BUN) / Urea test would be represented as BUN [mg/dL] for the regions used to conventional results (US, Latin America) and as Urea [mmol/L] for the regions used to SI (the international system of units) results. Therefore, both BUN and Urea parameters will be included in the data.

BUN is always reported as mg/dL and Urea as mmol/L. BUN and Urea are the same measurement in the lab and should be considered the same test. Hence, for the summary tables, it is expressed in SI units. Conversion to SI units includes the factor that incorporates a conversion from BUN to Urea as well as a conversion from mg/dL to mmol/L.

Listings of patients with notable laboratory values will be provided by laboratory parameter, treatment group, and patient number.

Additionally, box plot of change from baseline will be presented over time for ALT, AST, ALT/AST ratio, total bilirubin, creatinine, albumin,. ACR value will be considered missing if either the albumin or the creatinine values are missing. Similarly, PCR will be considered missing if either the protein or the creatinine values are missing.

2.8 Other safety data

2.8.1 ECG and cardiac imaging data

ECG measurements include heart rate, QT interval, RR interval, PR interval, QRS duration, and Fridericia's QTc (calculated as $QTcF = QT / \sqrt[3]{RR}$ (in seconds), where $\sqrt[3]{}$ denotes the cube root).

ECG data measured more than 1 day after last intake of study drug are regarded as post treatment data and will not be summarized. All data will be included in the analyses regardless of rescue medication use.

Clinically relevant values

- The number and percentage of patients with newly occurring or worsening clinical relevant QTcF values (see [Table 2.8.1](#)) summarized at any time on treatment considering all post-baseline data from scheduled, unscheduled and premature discontinuation visits.

Table 2.8.1 Clinically relevant criteria for QTcF (Fridericia's formula)

ECG parameter (unit)	Clinically relevant range
Value considering newly occurring or worsening cases	
QTcF (msec)	≥ 450 (male)
QTcF (msec)	≥ 460 (female)
QTcF (msec)	> 500 (both)
Change from baseline	
QTcF	< 30
QTcF	30 – 60
QTcF	> 60

Clinically notable values

- A summary table will also be produced for number and percentage of subjects with notable QT and QTcF intervals (irrespective of the time point) using the following categories:
 - any treatment emergent (new) QTcF or QT interval ≥ 450 ms – 480 ms, > 480 ms – 500 ms or > 500 ms
 - QTcF or QT increase from baseline of ≥ 30 ms – < 60 ms, ≥ 60 ms
 - QTcF and QT increase from baseline of ≥ 30 ms plus QTcF interval ≥ 450 ms, > 480 ms or > 500 ms
 - QTcF increase from baseline of ≥ 60 ms plus QTcF interval ≥ 450 ms, > 480 ms or > 500 ms
- The number and percentage of subjects with noteworthy PR, QRS and HR interval changes will be reported using the below categories:
 - New PR > 200 ms to ≤ 220 ms; and > 220 ms
 - New QRS > 110 ms to ≤ 120 ms; and > 120 ms
 - PR increase $> 25\%$ to a value > 200 ms
 - QRS increase $> 25\%$ to a value > 120 ms
 - HR decrease $> 25\%$ to a HR < 50 bpm
 - HR increase $> 25\%$ to a HR > 100 bpm

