- QAW039 has been well tolerated in populations studied to date at total daily doses up to 500 mg given for up to 12 weeks. In the 10 completed studies, 16 patients reported 17 SAEs, no deaths due to SAEs were reported, and 5 discontinuations due to SAEs were reported. Of the 16 patients reporting SAEs, 12 patients reported 13 events, 2 patients reported 2 events and 2 patients reported 2 events in the QAW039, placebo, and montelukast treatment groups, respectively. There were no SAEs with a suspected causal relationship to QAW039. There have been no adverse events of idiopathic drug reactions.
- Cardiovascular risks: Transient, increases in heart rate were observed in a cardiovascular safety pharmacology study in dogs. These changes were not associated with any significant alterations in blood pressure, ECG interval duration, morphology or rhythm or any structural changes in cardiac tissues. No cardiac findings have been identified in the healthy volunteer and patient studies completed to date apart from an observed imbalance in the frequency of post-randomization cardiac adverse events in study [CQAW039A2206] with a higher incidence in the QAW039 treatment group (1.7%) compared with either placebo (0.7%) or montelukast (0%) treated patients. The cardiac events comprised a number of different non-serious arrhythmias and one serious adverse event of pericarditis not suspected to be related to study drug by the Investigator. Three of the events in the QAW039 treatment groups occurred during the washout period and

resolved on treatment. Based on the inability to identify discernable trends with QAW039 dose, regimen, time-of-onset, patient age and gender, concomitant medication, event type and following detail ECG review, it was considered that these were most probably coincidental events without a causal association to study drug. A formal QTc study has not been completed for QAW039. Monitoring for changes in vital signs, ECGs and biochemical parameters will be conducted.

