#### 8.4.2 Electrocardiogram (ECG)

ECGs will be measured according to the assessment schedule in [Table 8-1](#). ECGs must be recorded after 10 minutes rest in the supine position to ensure a stable baseline. The preferred sequence of cardiovascular data collection during study visits is ECG collection first, followed by vital signs. The Fridericia QT correction formula (QTcF) should be used for clinical decisions.

Single 12-lead ECGs will be collected using the sites own ECG machines and key parameters and the original trace available within the source data.

For any ECGs with subject safety concerns, two additional ECGs must be performed to confirm the safety finding. A monitoring or review process should be in place for clinically significant ECG findings throughout the study and especially at baseline before administration of study treatment. Clinically significant abnormalities must be recorded on the CRF as either medical history/current medical conditions or adverse events as appropriate.

Any identifier details must be redacted e.g subject initials, date of birth.

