### **12-lead ECG**

The notable ECG abnormalities will be summarized for following ECG variables,QT interval, RR interval, PR interval, QRS duration, heart rate, and Friedericia's QTc.

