### 16.1 Appendix 1: Clinically notable laboratory values and vital signs

The central laboratory will flag laboratory values falling outside of the normal ranges on the central laboratory reports. Investigators are responsible for reviewing these abnormal values for clinical significance, signing the laboratory reports to indicate their review, and reporting values considered clinically significant in the appropriate electronic case report form (eCRF).

Any clinically significant abnormal laboratory value should be evaluated and followed-up by the Investigator until normal or a cause for the abnormality is determined.

See [Section 16.2](#) for specific liver event and laboratory test trigger definitions and follow-up requirements. See [Section 16.3](#) for specific renal alert criteria and actions.

For electrocardiograms (ECGs), a notable QTc value is defined as a QTcF (Fridericia) interval of  $\geq 450$  msec for males or  $\geq 460$  msec for females. All ECGs will be assessed locally at site and with assessment of clinical relevance and continuance of the patient being confirmed by the Investigator.

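### SAP 2.8.1: the 'clinically notable' QT list does not match Protocol 16.1 or Table 2.8.1, and its third row loses joint QTcF cases when heart rate rises (minor)

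*SAP*

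**What the plan says.** Protocol 16.1 (Appendix 1) states that "a notable QTc value is defined as a QTcF (Fridericia) interval of" at least 450 ms for males or 460 ms for females. Protocol 8.4.2 adds: "The Fridericia QT correction formula (QTcF) should be used for clinical decisions". For the analysis, the 12-lead ECG paragraph of Protocol 12.5.1 says: "The notable ECG abnormalities will be summarized for following ECG variables,QT interval, RR interval, PR interval", and goes on to QRS duration, heart rate and Fridericia's QTc. Uncorrected QT is therefore a planned summary variable.

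SAP 2.8.1 contains two QT summaries:

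- **Table 2.8.1 (clinically relevant values).** QTcF only: ≥ 450 ms male, ≥ 460 ms female, > 500 ms for both. QTcF change is banded < 30, 30–60 and > 60 ms.
- **A list of clinically notable values.** Its four QT rows are numbered here for reference:
  - Row 1: "any treatment emergent (new) QTcF or QT interval ≥ 450 ms" up to 480 ms, then > 480 to 500 and > 500 ms, with no split by sex.
  - Row 2: a rise in QTcF or QT of ≥ 30 to < 60 ms, or ≥ 60 ms.
  - Row 3: "QTcF and QT increase from baseline of ≥ 30 ms plus QTcF interval ≥ 450 ms", > 480 or > 500 ms.
  - Row 4: a QTcF rise of ≥ 60 ms with the same three QTcF levels and no condition on QT.

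SAP section 4 declares no change from the protocol's analyses.

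**The concern.** QTcF exists to remove the effect of heart rate on QT. A row that also demands a rise in raw QT brings that effect back: when the heart speeds up, raw QT shortens and can cancel a real QTcF increase. A row that accepts either measure has the reverse problem, because a slower heart lengthens raw QT with no change in QTcF. The word 'notable' also has one meaning in Protocol 16.1 and another in the SAP.

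The setting makes heart rate relevant. Protocol 4.5 says: "Transient, increases in heart rate were observed in a cardiovascular safety pharmacology study in dogs". It also reports a cardiac adverse event imbalance in an earlier asthma study (1.7% on QAW039, 0.7% on placebo) and says that no formal QTc study has been completed. Protocol Table 8-1 schedules one ECG during treatment, at the end-of-treatment visit, and 8.4.2 makes it a single recording. With so few ECGs, the categories should mean what their labels say.

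**Working it through.** The documents state no figure that depends on these categories, so there is none to reproduce. The check applies the SAP's own formula to example ECGs.

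**Inputs.** From SAP 2.8.1: QTcF = QT / RR^(1/3), RR in seconds. With RR = 60/HR, QT = QTcF × (60/HR)^(1/3). All patient values below are assumptions chosen for illustration.

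**1. Row 3 when heart rate rises.** HR 60 to 75 bpm, QTcF 420 to 455 ms (+35).
- Before: RR = 1.0, so QT = 420.0 ms.
- After: RR = 0.8, 0.8^(1/3) = 0.9283, so QT = 455 × 0.9283 = 422.4 ms.
- Raw QT rises by 2.4 ms, below 30.

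| Category | Counted? |
|---|---|
| Row 1 (QTcF ≥ 450) | yes |
| Row 2 (QTcF rise 30 to < 60) | yes |
| Row 3 (joint, literal reading) | **no** |
| Row 4 (QTcF rise ≥ 60) | no |
| Table 2.8.1, change 30–60 | yes |
| Table 2.8.1, value | yes if male; no if female (455 < 460) |

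**2. How large a heart-rate change is needed.** Start at HR 60 with QT = QTcF = 410 ms and let QTcF rise by d. Row 3 fails when (410 + d) × (60/HR)^(1/3) < 440, that is, when HR > 60 × ((410 + d)/440)³.
- d = 40 (QTcF 450): 60 × (450/440)³ = 64.2 bpm.
- d = 59 (QTcF 469): 60 × (469/440)³ = 72.7 bpm.
- d = 60 (QTcF 470): about 73 bpm, but row 4 counts this patient.

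The loss is therefore confined to QTcF rises of 30 to < 60 ms. For the smaller of these, a change of about 4 bpm is enough.

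**3. Rows 1 and 2 when heart rate is low or falls.**
- Row 2: QT 400 ms at 75 bpm gives QTcF = 400 / 0.9283 = 430.9 ms. At 60 bpm with QTcF unchanged, QT = 430.9 ms. Raw QT rises by 30.9 ms, which is a row 2 case with no QTcF change.
- Row 1: a new raw QT of 450 ms corresponds to QTcF 408.9 ms at 45 bpm, 423.5 ms at 50 bpm and 437.1 ms at 55 bpm. All lie below the Protocol 16.1 limits.

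**4. Sex-blind limit.** A woman with a new QTcF of 450–459 ms is notable in row 1 and not under Protocol 16.1. The mismatch can also run the other way. A woman at 455 ms is eligible, since exclusion criterion 5 starts at 460 ms. If she rises to 465 ms she becomes notable under Protocol 16.1, but she was already in row 1's first band at baseline and may not count as new there. Table 2.8.1 would count her.

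**5. Change bands.** A QTcF rise of exactly 60 ms falls in 30–60 in Table 2.8.1 and in ≥ 60 in row 2.

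**6. Weight of one patient.** 1/31 = 3.2 percentage points of a planned arm.

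**The case against.** A reader might infer that the SAP's ECG tables hide QTcF prolongation whenever heart rate rises. The documents do not support that. Rows 1 and 2 accept QTcF on its own, row 4 uses QTcF only, and Table 2.8.1 already applies the protocol's sex-specific QTcF limits and bands the QTcF change. The patient in step 1 is missing from row 3 alone. This part of the objection stands and sets the size of the point.

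A reader might also infer that raw QT has no place in the list. Protocol 12.5.1 names QT interval among the variables for the notable-ECG summary, so removing it would create a new discrepancy. Protocol 16.1 defines a notable QTc, and 8.4.2 concerns clinical decisions; neither forbids tabulating QT. This stands too. The protocol does not, however, ask for QT and QTcF to be merged into one count, and it gives no limit for raw QT.

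The list is introduced as covering QT and QTcF intervals, so row 3 could mean that each measure is reported separately. That is possible. Against it, rows 1 and 2 use 'or' where row 3 uses 'and', which favours the literal reading. If separate reporting was meant, the text needs to say so.

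Finally, the risk context should not be overstated. Protocol 4.5 says that the changes in dogs came without significant alterations in ECG interval duration, and that the cardiac events were judged most probably coincidental. The SAP also tabulates marked heart-rate changes, which helps in interpreting a rate-driven QT shift, though a change such as 75 to 60 bpm (20%) is below its > 25% criterion.

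**Conclusion.** Wrong as written, and minor. Read literally, row 3 drops patients with a QTcF rise of 30 to < 60 ms and QTcF ≥ 450 ms when heart rate also rises. It is the only category that joins such a rise with a high absolute value, so for these patients the joint finding appears in no planned table, although its two parts are counted separately. The pooled rows can count patients with no QTcF change. The 450 ms limit departs from Protocol 16.1 for women without being declared, and a 60 ms rise has two classes within one section.

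The size rests on assumed heart rates and intervals, because the documents give no ECG distributions. The row 3 point also rests on reading 'and' as a conjunction. The sex limit and the change bands need neither assumption. Nothing here touches the primary analysis, and the summaries taken together still report QTcF prolongation.

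**What to change.** In SAP 2.8.1:

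1. Base row 3 on the QTcF increase alone, as row 4 does.
2. In rows 1 and 2, replace the pooled 'QTcF or QT' with separate QTcF and QT rows. Keep QT, because Protocol 12.5.1 lists it.
3. For the first QTcF category, use the Protocol 16.1 limits (≥ 450 ms male, ≥ 460 ms female), then > 480 and > 500 ms. The protocol gives no limit for raw QT, so label the SAP's own QT limits as such.
4. Use one set of change bands in Table 2.8.1 and in the list, so that a rise of exactly 60 ms has one class.

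These changes concern tabulation only. The cost is SAP wording and table shells, with no change to data collection, visits or sample size.
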